13.6.2. Study Population

Treatment Compliance

 • Treatment compliance will be calculated based on the formula: $\text{Treatment Compliance} = \text{Number of Actual Doses} / (\text{Planned Treatment Duration in Days} * \text{Frequency})$ • Frequency is 2 for BID and 1 for QD. Treatment compliance could be greater than 100% if there are events of overdose. Cumulative compliance (since Day 1) at each visit will be calculated.
Extent of Exposure

 • Number of days of exposure to study drug will be calculated based on the formula: $\text{Duration of Exposure in Days} = \text{Treatment Stop Date} - (\text{Treatment Start Date}) + 1$ • Participants who were randomized but did not report a treatment start date will be categorised as having zero days of exposure. • The cumulative dose will be based on the formula: $\text{Cumulative Dose} = \text{Sum of (Number of Days x Total Daily Dose)}$ • If there are any treatment breaks during the study, exposure data will be adjusted accordingly.

13.6.3. Safety

Laboratory Parameters

 • If a laboratory value which is expected to have a numeric value for summary purposes, has a non-detectable level reported in the database, where the numeric value is missing, but typically a character value starting with '<x' or '>x' (or indicated as less than x or greater than x in the comment field) is present, the number of significant digits in the observed values will be used to determine how much to add or subtract in order to impute the corresponding numeric value. 
 ○ Example 1: 2 Significant Digits = '< x' becomes x – 0.01 ○ Example 2: 1 Significant Digit = '> x' becomes x + 0.1 ○ Example 3: 0 Significant Digits = '< x' becomes x – 1

ECG Parameters

RR Interval

 • If RR interval (msec) is not provided directly, then RR can be derived as: [1] If QTcF is machine read, then: $RR = \left[\left(\frac{QT}{QTcF} \right)^3 \right] * 1000$ • If ECGs are manually read, the RR value preceding the measurement QT interval should be a collected value. THEN do not derive.
--

Corrected QT Intervals

 • When not entered directly in the ClinBase, corrected QT intervals by Fredericia's (QTcF) formula will be calculated in msec, depending on the availability of other measurements. • IF RR interval (msec) is provided then missing QTcF will be derived as: $QTcF = \frac{QT}{\sqrt[3]{\frac{RR}{1000}}}$
--

13.6.4. Pharmacokinetic

PK Parameters
The PK Population will include all subjects who undergo PK sampling and have evaluable PK assay results. 
• See Table 2. Derived Pharmacokinetic Parameters (Primary end points) and Table 3. Derived Pharmacokinetic Parameters (Secondary end points) for derived Pharmacokinetic parameters

13.7. Appendix 7: Reporting Standards for Missing Data

13.7.1. Premature Withdrawals

Element	Reporting Detail
General	
 • Subject study completion (i.e. as specified in the protocol) was defined as 'A participant is considered to have completed the study if he/she has completed all phases of the study including or the last scheduled procedure shown in the SoA.' • Withdrawn subjects may be replaced in the study. • All available data from participants who were withdrawn from the study will be listed and all available planned data will be included in summary tables and figures, unless otherwise specified.

13.7.2. Handling of Missing Data

Element	Reporting Detail
General	
 • Missing data occurs when any requested data is not provided, leading to blank fields on the collection instrument: 
 ○ These data will be indicated by the use of a "blank" in subject listing displays. Unless all data for a specific visit are missing in which case the data is excluded from the table. ○ Answers such as "Not applicable" and "Not evaluable" are not considered to be missing data and should be displayed as such.
Outliers	
 • Any participants excluded from the summaries and/or statistical analyses will be documented along with the reason for exclusion in the clinical study report.

13.7.2.1. Handling of Missing and Partial Dates

Element	Reporting Detail
General	
 • Partial dates will be displayed as captured in subject listing displays.
Adverse Events	
 • The Clinbase allows for the possibility of partial dates (i.e., only month and year) to be recorded for AE start and end dates; that is, the day of the month may be missing. In such a case, the following conventions will be applied for calculating the time to onset and the duration of the event: 
 ○ Missing Start Day: First of the month will be used unless this is before the start date of study treatment; in this case the study treatment start date will be used and hence the event is considered On-treatment as per Appendix 4: Study Phases ○ Missing Stop Day: Last day of the month will be used, unless this is after the stop date of study treatment; in this case the study treatment stop date will be used. • Completely missing start or end dates will remain missing, with no imputation applied. Consequently, time to onset and duration of such events will be missing.
Concomitant Medications/Medical History	
 • Partial dates for any concomitant medications recorded in the CRF will be imputed using the following convention: 
 ○ If the partial date is a start date, a '01' will be used for the day and 'Jan' will be used for the month ○ If the partial date is a stop date, a '28/29/30/31' will be used for the day

Element	Reporting Detail
	
(dependent on the month and year) and 'Dec' will be used for the month.
 
 • The recorded partial date will be displayed in listings. • For each period in crossover design: 
 ○ If start date is completely missing, then we assume the medication has been taken from the beginning of the study ○ If stop date is completely missing, then we assume the medication has been taken until the end of the study

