6.3. Measures to Minimize Bias: Randomization and Blinding

6.3.1. Randomization

Study using Pre-Coded Randomization provided to site	Before treatment begins at the beginning of each part of the study, participants will be assigned a unique number (randomization number) in ascending numerical order at the study site. The randomization number encodes the participant's assignment to the respective arms of the study, according to the randomization schedule generated prior to the study by the Clinical Statistics Department at GSK. Each participant will be dispensed blinded study intervention, labeled with his/her unique randomization number throughout the study.
---	--

In Part A, approximately 9 participants in each cohort will be randomized to one of 3 treatment sequences (AAP, APA & PAA, where A represents an active dose of GSK3439171 and P represents placebo). Within each period, allocation of active (A) to placebo (P) treatment will be 2:1. Within a cohort, an increasing dose of GSK3439171A will be administered in each period as illustrated in the table below. Planned doses are provided in Section 6.6. At each dose level, sentinel dosing will be employed, such that one subject is dosed with placebo and another with active dose of GSK3439171A and followed for 48 hr prior to the rest of the subjects receiving their randomized treatment.

Cohort	Sequence	Period 1	Period 2	Period 3
Cohort 1	AAP	D1	D2	Placebo
	APA	D1	Placebo	D3
	PAA	Placebo	D2	D3
Cohort 2	AAP	D4	D5	Placebo
	APA	D4	Placebo	D6
	PAA	Placebo	D5	D6
Cohort 3	AAP	D7	D8	Placebo
	APA	D7	Placebo	D9
	PAA	Placebo	D8	D9

In each cohort of Part B, approximately 12 participants will be randomized to receive either GSK3439171A or placebo in a parallel design using a 3:1 allocation ratio. Participants will receive a single dose followed by a 72 hr assessment period and then will receive daily repeat doses until the end of the study.

Dose Cohort	Regimen
B1	R1 mg GSK3439171A or placebo QD or BID
B2 ¹	R2 mg GSK3439171A or placebo QD or BID
B3 ¹	R3 mg GSK3439171A or placebo QD or BID

1. Dose levels for Cohorts will be determined based on real-time analysis of the safety, tolerability, PK, and preliminary PD data from Part A and therefore may be adjusted from predicted dose levels listed.

QD – Once daily

BID- Twice daily

Regimen	Period 1	Period 2
X	GSK3439171A ¹ administered in the fasted state	GSK3439171A ¹ administered after a high fat meal

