13.4. Appendix 4: Study Phases and Treatment Emergent Adverse Events

13.4.1. Study Phases

Assessments and events will be classified according to the time of occurrence relative to study treatment

Study Phase	Definition
Pre-Treatment	Date ≤ Study Treatment Start Date
On-Treatment	Study Treatment Start Date < Date ≤ Study Treatment Stop Date + 3 days
Post-Treatment	Date > Study Treatment Stop Date + 3 days

Note: Estimated half-life of GSK3439171 is approx. 13 hours. The maximum of (5 half-lives ~ 65 hours ~ 3days) and after the Study Treatment End Date, lag time have been considered to be 3 days to define the end of treatment phase.

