13.6. Appendix 6: Derived and Transformed Data

13.6.1. General

Multiple Measurements at One Analysis Time Point

 • Mean of the measurements will be calculated and used in any derivation of summary statistics but if listed, all data will be presented. • If there are two values within a time window the value closest to the target day for that window will be used. If values are the same distance from the target, then the mean will be taken. • Participants having both High and Low values for Normal Ranges at any post-baseline visit for safety parameters will be counted in both the High and Low categories of “Any visit post-baseline” row of related summary tables. This will also be applicable to relevant Potential Clinical Importance summary tables.
Study Day and Period Study Day

In PART A and C, Period Study day is calculated as the number of days from first Dose Date in the period for each subject as follows:
 
 • Ref Date = Missing → Period Study Day = Missing • Ref Date < First Dose Date in the period → Period Study Day = Ref Date – First Dose Date in the period • Ref Date ≥ First Dose Date in the period → Period Study Day = Ref Date – First Dose Date in the period + 1 
In Part A, B & C: Study day is calculated as the number of days from First Dose Date in each Cohort for each subject as:
 
 • Ref Date = Missing → Study Day = Missing • Ref Date < First Dose Date → Study Day = Ref Date – First Dose Date • Ref Date ≥ First Dose Date → Study Day = Ref Date – (First Dose Date) + 1
Change from baseline and Percentage change from baseline definition

Change from Baseline = Post-Dose Visit Value – Baseline (For Part A & C, corresponding period baseline should be considered as baseline)
 
Percentage Change from Baseline = ((Post-Dose Visit Value – Baseline)/Baseline)*100 (For Part A & C, corresponding period baseline should be considered as baseline)
 
 • Unless otherwise specified, the baseline definitions specified in Section 5.2 Baseline Definition will be used for derivations for endpoints / parameters and indicated on summaries and listings • Unless otherwise stated, if baseline data is missing no derivation will be performed and will be set to missing
Displays

- Compound ID should be used as GSK3439171 for the displays

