13.12.5. Safety Tables

- The requirements for each display (i.e. IDSL, ICH, FDAAA etc) specified in the programming notes may be retained, all other red reference notes should be deleted.
- Select appropriate standard based on study design (i.e. parallel vs cross-over), when applicable.
- Suggested IDSL shells are noted in the third column, but other IDSL shells may be used, as appropriate

CONFIDENTIAL

209275

- The ADaM datasets for the Core Study Population/Safety displays can be found in the IDSL Library under Reference → Statistical Displays
→ ADaM Datasets for Core RAP Displays

Safety: Tables					
No.	Population	IDSL / Example Shell	Title	Programming Notes	Deliverable [Priority]
Adverse Events (AEs)					
3.1.	Safety	CP_AE1x	Summary of All Adverse Events by System Organ Class and Preferred Term - Part A		SAC
3.2.	Safety	CP_AE1p	Summary of All Adverse Events by System Organ Class and Preferred Term - Part B		SAC
3.3.	Safety	CP_AE1p	Summary of All Adverse Events by System Organ Class and Preferred Term by Study Phase - Part B		SAC
3.4.	Safety	CP_AE1x	Summary of All Adverse Events by System Organ Class and Preferred Term - Part C		SAC
3.5.	Safety	AE5B	Summary of All Adverse Events by Maximum Grade by System Organ Class and Preferred Term – Part A		SAC
3.6.	Safety	AE5B	Summary of All Adverse Events by Maximum Grade by System Organ Class and Preferred Term – Part B		SAC
3.7.	Safety	AE5B	Summary of All Adverse Events by Maximum Grade by System Organ Class and Preferred Term – Part C		SAC
3.8.	Safety	CP_AE1x	Summary All Drug-Related Adverse Events by System Organ Class and Preferred Term- Part A		SAC
3.9.	Safety	CP_AE1p	Summary All Drug-Related Adverse Events by System Organ Class and Preferred Term - Part B	As 3.1 notes.	SAC

Safety: Tables					
No.	Population	IDSL / Example Shell	Title	Programming Notes	Deliverable [Priority]
3.10.	Safety	CP_AE1x	Summary All Drug-Related Adverse Events by System Organ Class and Preferred Term - Part C	As 3.1 notes.	SAC
3.11.	Safety	AE15	Summary of Common (>=10%) Non-serious Adverse Events by System Organ Class and Preferred Term (Number of Participant and Occurrences) – Part A	
FDAAA, EudraCT Disclosure display
 
Common' to be defined by study/project team. For studies with very few events/participants, listing is sufficient: discuss this option with your disclosure representative.
	SAC

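### The SAP rule for an adverse event with a missing start day ignores dosing periods in crossover Parts A and C, so such events in Periods 2 and 3 are usually dated before that period's own dose

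*SAP*

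**What the plan says.** SAP 13.7.2.1 covers AEs for which only month and year are known. For a missing start day, "First of the month will be used unless this is before the start date of study treatment"; otherwise, "in this case the study treatment start date will be used and hence the event is considered On-treatment". The stated purpose is limited: "the following conventions will be applied for calculating the time to onset and the duration of the event". Nothing in the AE row refers to periods.

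Other parts of the plan do:

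- The concomitant medication row of the same table has a clause that begins "For each period in crossover design".
- SAP 13.6.1 counts period study days in Parts A and C from the first dose date in the period, and it sets period baselines: "For Part A & C, corresponding period baseline should be considered as baseline".
- Protocol 6.3.1 makes the order of periods the order of doses: "Within a cohort, an increasing dose of GSK3439171A will be administered in each period". The sequence table gives D3, D6 and D9 in Period 3 only.

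SAP Appendix 4 (13.4.1) says "Assessments and events will be classified according to the time of occurrence relative to study treatment", and uses one start date and one stop date. It classes a date on or before the study treatment start date as Pre-Treatment.

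The main Part A AE display is Table 3.1, "Summary of All Adverse Events by System Organ Class and Preferred Term - Part A". Neither it nor SAP 7.1 says how an AE is assigned to a period or dose.

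**The concern.** The rule suits Part B, where there is one treatment and one start date. In a crossover, an event known only to fall in a given month may belong to any period that overlaps that month. Taking the earliest date that the month and the first dose allow will often place the event in a period when the participant was on another dose or on placebo.

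Two things are at stake. Time to onset and duration, which the rule is written to produce, are wrong for these events. And if imputed dates also decide the dose column, the error has a direction: events after a cohort's highest dose move to lower doses or placebo. Safety is a primary objective, it is judged by descriptive comparison with placebo, and about six participants receive each active dose in Part A. One displaced event would show.

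**Working it through.** The documents give no figure on this point, so there is none to reproduce. The check applies the rule as written.

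**Inputs**

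- Rule: imputed date = later of (first of the onset month, Period 1 dose date). SAP 13.7.2.1.
- AE collection runs from the start of intervention to follow-up, about 14 ± 1 days after the last dose. Protocol 8.3.1 and Schedule of Activities.
- Part A dose gap: about 7 days (Protocol 4.1) to about two weeks (Protocol 4.2). With 14-day gaps, 30 + 2 × 14 + 14 = 72 days = 10.3 weeks, close to the protocol's 10 weeks. Seven-day gaps give 58 days = 8.3 weeks.
- In-house stay in Part A: Day -2 to Day 4 of each period. Protocol 4.1.
- Assumptions: first doses spread evenly over the calendar; onset lag spread evenly over the stated days.

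**Direction.** True onset is never before its own month's first day, nor before the Period 1 dose. So imputed date ≤ true onset, always. If an event belongs to the last dose on or before its imputed date, Period 1 events stay in Period 1, Period 2 can lose and gain, and Period 3 can only lose. Under sequence AAP, Period 3 is placebo, and it loses events in the same way.

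**Size.** An event with onset L days after its own dose keeps an imputed date in its own period only if a first of the month falls within the L + 1 days from dose to onset. A four-year cycle has 48 such days in 1,461, so

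share dated before own dose = 1 − (L + 1) × 48/1461.

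This gives 96.7% at L = 0, 50.7% at L = 14 and 47.4% at L = 15. Averaged over lags:

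| Onset assumed | Period 2, gap 7 / 10 / 14 days | Period 3 |
|---|---|---|
| In-house, days 0–3 (mean L + 1 = 2.5) | 91.8% at each gap | 91.8% |
| Whole period (mean L + 1 = 4 / 5.5 / 7.5; Period 3, days 0–14: 8) | 86.9 / 81.9 / 75.4% | 73.7% |
| After discharge, from day 4 (mean 6 / 7.5 / 9.5; Period 3, days 4–15: 10.5) | 80.3 / 75.4 / 68.8% | 65.5% |
| After discharge, period taken to begin at Day -2 admission | 77.0 / 72.1 / 65.5% | 58.9% |

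Enumeration of every start date over four years gives the same values. For Part C, Period 2 takes the Period 3 values of the first three rows (65.5% to 91.8%). Its admission is on Day -1, so the last row becomes 1 − (10.5 + 1) × 48/1461 = 62.2%.

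**Example.** Take Cohort 2, sequence PAA, with the doses in SAP 5.1 and assumed dosing on 3, 10 and 17 March: placebo, 120 mg, 180 mg. An AE that began on 20 March is recorded as March. Imputed onset is the later of 1 March and 3 March, so 3 March. That is the placebo dose day, 14 days before the event's own dose and 17 days before true onset. With the period's dose date as reference, it is the later of 1 March and 17 March, so 17 March.

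**With the period reference.** All events in Periods 1, 2 and 3 stay in their own period for every gap and lag tried.

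**Study phase.** With whole-period onset and gaps of 7 to 14 days, the imputed date equals the Period 1 dose date for 79–90% of such Period 1 events, 33–67% of Period 2 and 1–31% of Period 3. SAP 13.7.2.1 calls these On-treatment. Appendix 4 makes them Pre-Treatment.

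**The case against.** The strongest reply is that the convention is written for time to onset and duration, not for assigning treatment. No sentence in the SAP sends an imputed date into a dose column. AE analyses follow the sponsor's core data standards, Part A uses a separate crossover table shell, and the Part A Schedule of Activities sets out AE review for each dosing period. If the case report form records the period, the dose tables can be right whatever date is imputed. This stands. A reader might infer that the Part A tables will under-count AEs at the top doses. The documents do not support that: the standards and the form are not available, and the shift occurs only if AEs are assigned by imputed date.

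Nor are 59–92% of all AEs in these periods misdated. The percentages apply only to events with a missing start day. No document gives their frequency, and supervised in-house days make them likely to be few. The in-house row of the table is therefore the least relevant, and the post-discharge rows the most. Listings show partial dates as captured, so affected events remain visible. In Part C both periods use the same dose (60 mg in SAP 5.1), so only the fed/fasted label could change.

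The medication clause is also a weak comparison. It deals with completely missing dates and defaults to the whole study, so it is no model for AEs.

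Finally, the SAP does not define the study treatment start date for crossover parts, so someone could read it as the period's dose. But 13.6.1 uses a different term for that date, and the AE row does not use it. The need to choose a reading is itself a reason to state one.

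**Conclusion.** The point holds for time to onset and duration. As written, the rule never dates an event too late and usually dates a Period 2 or 3 event before the dose it followed: about 59% to 92% of missing-day events over the scenarios tried, falling to about half only for onset two weeks after the last dose. An onset moved earlier also lengthens the derived duration whenever the stop date is known. These figures assume that the reference is the Period 1 dose and that dosing is spread evenly over the calendar.

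The loss of events from each Part A cohort's top dose is conditional on assignment by imputed date, for which the SAP offers no alternative rule. The number of events is unknown and probably small, which makes this a modest correction. The conflict over study phase between 13.7.2.1 and Appendix 4 does not depend on any of these assumptions.

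**What to change.** In SAP 13.7.2.1, for Parts A and C:

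1. Impute a missing AE start day as the later of the first of the month and the first dose date, as used in 13.6.1, of the period in which the event was recorded.
2. State that AEs are assigned to treatment by the recorded period.
3. If the period cannot be identified, flag the event, list it with every treatment compatible with the known month, and check the dose tables with it counted under each.

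Do not default to the latest compatible period as a cautious choice. That is the mirror error: with whole-period onset, a Period 1 or 2 event stays put only if a first of the month falls between onset and the next dose. So 1 − 7.5 × 48/1461 = 75.4% (14-day gap) to 1 − 4 × 48/1461 = 86.9% (7-day gap) would move to a later period, and under AAP some would move from active drug to placebo.

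Keep the present start-day reference for Part B. Reconcile 13.7.2.1 with Appendix 4, so that an AE dated to the treatment start date has one study phase.

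The cost is a few sentences and a small change to the AE derivation. No new data are needed where the record carries the period; otherwise item 3 applies.

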13.7.2.2. Handling of PK Concentration Data

Element	Reporting Detail
General	
 • Missing data occurs when any requested data is not provided, leading to blank fields on the collection instrument. • These data will be indicated by the use of a “blank” in subject listing displays. Unless all data for a specific visit are missing in which case the data is excluded from the table. • Answers such as “Not applicable” and “Not evaluable” are not considered to be missing data and should be displayed as such.
Outliers	Any subjects excluded from the summaries and/or statistical analyses will be documented along with the reason for exclusion in the clinical study report.

13.7.2.3. Handling of Missing Data for Statistical Analysis

Element	Reporting Detail
Imputation	
 ○ No imputation will be performed for missing data

13.8. Appendix 8: Values of Potential Clinical Importance

13.8.1. Laboratory Values

Haematology				
Laboratory Parameter	Units	Category	Clinical Concern Range	
			Low Flag (< x)	High Flag (>x)
Hematocrit	Ratio of 1	Male		0.54
		Female		0.54
		Δ from BL	↓0.075	
Haemoglobin	g/L	Male		180
		Female		180
		Δ from BL	↓25	
Lymphocytes	x10 ⁹ /L		0.8	
Neutrophil Count	x10 ⁹ /L		1.5	
Platelet Count	x10 ⁹ /L		100	550
While Blood Cell Count (WBC)	x10 ⁹ /L		3	20

Clinical Chemistry				
Laboratory Parameter	Units	Category	Clinical Concern Range	
			Low Flag (< x)	High Flag (>x)
Albumin	g/L		30	
Calcium	mmol/L		2	2.75
Creatinine	umol/L	Δ from BL		↑ 44.2
Glucose	mmol/L		3	9
Magnesium	mmol/L		.5	1.23
Phosphorus	mmol/L		.8	1.6
Potassium	mmol/L		3	5.5
Sodium	mmol/L		130	150
Creatine Kinase (CK)				>500 U/l
Liver Function				
Test Analyte	Units	Category	Clinical Concern Range	
ALT/SGPT	U/L	High	≥ 2x ULN	
AST/SGOT	U/L	High	≥ 2x ULN	
AlkPhos	U/L	High	≥ 2x ULN	
T Bilirubin	μmol/L	High	≥ 1.5x ULN	
T. Bilirubin + ALT	μmol/L U/L	High	1.5xULN T. Bilirubin + ≥ 2x ULN ALT	

